5.3.5.2. Change from baseline in EDSS

The ponesimod baseline value is flagged in the ADaM dataset.

Absolute and percentage change from ponesimod baseline are derived for all post-(applicable) baseline EDSS assessments. All nominal visits are re-windowed based on the visit schedule in Section 5.1.7. See footnote on table, Weeks 1, 2, 4, 8, 12, 16 and 20 are not defined for EDSS. No last-on-treatment visit, follow-up visits or last follow-up visit are defined for EDSS as an intent-to-treat approach is used for efficacy.

5.3.6. Analysis of Neurological variables

5.3.6.1. Time to 24-week CDA

Time to 24-week CDA is analyzed for AP3 on the PAS, using the Kaplan-Meier method and Cox proportional hazards model as described for time to first relapse in Section 5.3.4.1.

5.3.6.2. Change from baseline in EDSS

The absolute EDSS score and change from ponesimod baseline in EDSS score by analysis visit and treatment group are summarized using descriptive statistics for AP3 on the PASA corresponding listing of EDSS / functional system (FS) scores and indicating start date of a CDA / confirmation of a CDA is produced for AP3 on the PAS.

5.3.8. Analysis of ophthalmological variables

Absolute values and absolute change from ponesimod baseline values by analysis visit and treatment group are summarized using descriptive statistics for AP3 on the OCT for retinal nerve fiber layer (RNFL) thickness, central foveal thickness, total macular volume and number of letters correctly read.

Absolute change from ponesimod baseline in central foveal thickness by analysis visit is summarized using descriptive statistics and frequency counts and percentages for the categorical change, for AP3 on the OCT.

A listing of all ophthalmological variables is produced for AP3 on the OCT.

5.4. Other Safety Analyses

All safety analyses will be based on the PAS based on actual intervention received, unless otherwise specified.

For all continuous safety variables, descriptive statistics by intervention group will include the N, mean, standard deviation, median, minimum, and maximum. Categorical variables will be summarized by intervention group using frequency counts and percentages.

Unscheduled visits are not presented in summary tables or figures by visit unless mapped to a windowed analysis visit [see Section 5.1.8]. Any unscheduled assessments that meet the predefined high/low criteria are flagged and may be included in the corresponding incidence tables.

The outputs summarizing abnormalities only use treatment-emergent data.

Summaries of safety assessments over time are presented by analysis visit (see Section 5.1.9 for derivation of analysis visit). In these summary tables by analysis visit, except for values at baseline and follow-up visits, only treatment-emergent values are displayed.

5.4.1. Exposure and Compliance

5.4.1.1. Exposure to study treatment

All ponesimod drug administration data is taken from the study drug log and stored in SDTM.EC. ECSTDTC where EC.ECCAT = 'STUDY DRUG INTAKE'. The two EC datasets are concatenated for the purposes of this analysis.

Ponesimod exposure (years) for any given exposure period is derived as:

-[(Treatment end date - ponesimod start date + 1 day) - (End date of pregnancy interruption - Start date of pregnancy interruption + 1 day)] / 365.25, for subjects with planned pregnancy interruption and restart of the treatment,

- (Treatment end date - ponesimod start date + 1 day) / 365.25, regardless of interruptions, for all other subjects.

Duration of planned pregnancy study drug interruption (days) is defined as: min (EOS date, end date of pregnancy interruption) – Start date of pregnancy interruption + 1 day
In case of multiple planned pregnancies, all intervals between start date and end date of each pregnancy interruption will be subtracted from exposure.

Duration of planned pregnancy is excluded from all definitions of exposure duration and compliance with study treatment.

The following variables are derived for ponesimod exposure:

	1	
Exposure period	Start date	End date
Ponesimod exposure	First administration of	Last administration of ponesimod in the
during the core study	ponesimod in the core study	core study
(years)		
Ponesimod exposure	First administration of	Last administration of ponesimod in TP1
during TP1 (years)	ponesimod TP1	_
Ponesimod exposure	First administration of	Last administration of ponesimod in TP2
during TP2 (years)	ponesimod TP2	_
Ponesimod exposure	First administration of	Last administration of ponesimod in TP3
during TP3 (years)	ponesimod TP3	
Ponesimod exposure	First administration of	Max of [last administration of ponesimod
during AP3 (years)	ponesimod (in core or TP1)	in the core study, last administration of
		ponesimod in TP1, last administration of
		ponesimod in TP2, last administration of
		ponesimod in TP31

Table 10: Ponesimod exposure variables

AP = Analysis Period; TP = Treatment Period.

If end date is missing on last record in EC (e.g., if a subject is lost to follow-up), then date of last administration is taken as DS.DSSDTC when DSSCAT = 'Study termination'.

For each of the variables defined in Table 10 above, the following corresponding exposure variables are derived:

- Ponesimod exposure over defined exposure period, categorized into the following intervals: ≤ 6 months, > 6 months and ≤1 year, > 1 year and ≤ 2 years, > 2 years and ≤ 3 years, > 3 years and ≤ 4 years, > 4 years and ≤ 5 years, > 5 years and ≤ 6 years, > 6 years and ≤ 7 years, > 7 years and ≤ 8 years, > 8 years and ≤ 9 years, > 9 years and ≤ 10 years, > 10 years and ≤ 11 years, > 11 years and ≤ 12 years, > 12 years.
- Cumulative duration of interruptions during the defined exposure period (days): the cumulative duration of interruptions is the sum of all interruptions during the period up to the date of last administration of ponesimod within the period (i.e., interruptions before the start of the next period are not included). Treatment interruption refers to any period during which the subject did not receive study treatment, i.e., one or more day without documented treatment intake (per the CRF Study Drug Log page). Each interruption is calculated as:

Re-start date of ponesimod treatment - end date of previous ponesimod treatment - 1;

• Ponesimod treatment exposure during the defined exposure period with interruptions excluded (years): ponesimod exposure over the defined exposure period - (cumulative duration of corresponding interruptions)/365.25).

- Number of treatment interruptions (> 3 days) during the defined exposure period: an interruption with a duration is > 3 days.
- **Cumulative duration of interruptions during the defined exposure period (days):** the cumulative duration of interruptions is the sum of all interruptions (of any duration duration) during the period.

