- Visit FU1 (Follow-up visit 1): 8 days after the last study drug intake.
- Visit FU2 (Follow-up visit 2): 30 days after the last study drug intake.
- Visit FU3 (Follow-up visit 3):
- 90 days after the last study drug intake.

Patients who discontinue study drug prematurely must have the corresponding Safety Follow-up visits after their last study drug intake.

These visits and assessments will also be conducted for patients who have switched to commercially available ponesimod.

End-of-study (EOS2/EOS3)

- End-of-study (EOS) visit 2 (EOS2) for an individual patient is reached 30 days after the last dose of study drug in TP1.
- Patients not enrolling into TP2 have to perform EOS2.
- EOS3 for an individual patient is reached 90 days after the last dose of study drug for patients that have enrolled into TP2 and TP3, if applicable.
- Patients not enrolling into TP3 have to perform EOS3.
- The maximum duration of this extension study for an individual patient is up to 649 weeks (636 weeks of treatment extension, and 90 days of follow-up).

Patients will follow the standard of care after completing the study.

EudraCT 2009-011470-15

EDMS-ERI-206617631

Ponesimod / ACT-128800 / JNJ-67896153 Multiple Sclerosis Protocol AC-058B202 Version 12 15 March 2022, page 57/179

Confidential

Figure 1: Study design

AC-058B201 (Core Study)		AC-058B202 (Extension Study)	
24 weeks	Up to 96 weeks	Up to 540 weeks	Up to 90 days
10 mg ponesimod ·	► 10 mg ponesimod	→ 10 mg ponesimod → 20 mg ponesimod	
20 mg ponesimod	► 20 mg ponesimod	→ 20 mg ponesimod → 20 mg ponesimod	
40 mg ponesimod ·	► 40 mg ponesimod	1:1 \checkmark 10 mg ponesimod \rightarrow 20 mg ponesimod 20 mg ponesimod \rightarrow 20 mg ponesimod	
	10 mg ponesimod	→ 10 mg ponesimod → 20 mg ponesimod	
Placebo -	→1:1:1 → 20 mg ponesimod	$\longrightarrow 20 \text{ mg ponesimod} \qquad \longrightarrow 20 \text{ mg ponesimod}$ $ 10 \text{ mg ponesimod} \qquad \longrightarrow 20 \text{ mg ponesimod}$	
	40 mg ponesimod	1:1 < 20 mg ponesimod → 20 mg ponesimod	
Transition	Ex	atension Treatment Periods	
Informed Consent	Period 1 Randomization	Period 2 Period 3	Follow-up*
Up to Visit 11 3 days Veek 24	Period 1 Visits: E1 until E13 Period 1 Week: 1 until 96	(EOT2) Period 2 / 3 Visits: P1 until EOT3 Period 2 / 3 Week: 1 until 540	

*Safety follow-up visits:

After treatment period 1: at 8 and 30 days after last dose of study drug

After treatment period 2 and treatment period 3: at 8, 30 and 90 days after last dose of study drug

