5. STATISTICAL ANALYSES

5.1. General Considerations

5.1.1. Dates, times and days

Core study treatment start date: date of first administration of study drug (ponesimod or placebo) in AC-058B201.

Extension study treatment start date: date of first administration of ponesimod in AC-058B202.

Ponesimod start date (PSD): date of first administration of ponesimod:

- for subjects randomized to ponesimod in the core study, this is the date of the first study drug administration in the core study.
- for subjects randomized to placebo in the core study and enter the extension, this is the date of the first study drug administration in the extension study.

Ponesimod EOT / ponesimod end date: defined as the latest study treatment end date as recorded on the Study Drug Log (ECENDTC in SDTM.EC where ECCAT = 'STUDY DRUG LOG').

Extension End-of-Treatment (eEOT) / **extension study treatment end date:** equal to the Ponesimod EOT / Ponesimod end date as defined above for subjects entering the extension study. Missing for subjects not entering the extension study.

Core End-of-Study (cEOS) date: the EOS date in the core study, defined as DSSTDTC in SDTM201.DS, where DSSCAT='STUDY TERMINATION'. If the subject died, then EOS date is set to death date, where death date is defined as SDTM201.DD.DDDTC.

Extension End-of-Study (eEOS) date: the EOS date in the extension study, defined as DSSTDTC in SDTM202.DS, where DSSCAT='STUDY TERMINATION'. If the subject died, then EOS date is set to death date, where death date is defined as SDTM202.DD.DDDTC. Missing for subjects not entering the extension study.

Last study date: defined as core EOS date for subjects who did not enter the extension study, and Extension EOS date for subjects who did enter the extension study.

Ponesimod Study Day: defined as the number of days elapsed since ponesimod start date (PSD) plus 1 (e.g., Ponesimod Study Day 1 is the day of first administration of ponesimod). For dates prior to ponesimod start date (PSD), study day is the negative number of days elapsed between the date under consideration and the day of first administration of ponesimod. Therefore, the ponesimod study day is always different from 0.

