5.1.4. Treatment-emergent definition

For the purpose of safety evaluations, the treatment-emergent period is defined as the time from first administration of ponesimod up to 15 days (inclusive) after last administration of ponesimod as study drug.

Assessments on the date of first intake of ponesimod are considered treatment-emergent, unless they are clearly documented to be prior to first intake of ponesimod.

Note that, as per Section 5.1.3, planned pregnancy interruption period is excluded from treatmentemergent definition and other related variables.

The period of planned pregnancy interruption will be excluded from the treatment-emergent period for subjects with planned pregnancy interruption and restart of the treatment prior to the EOS date. Therefore, the treatment-emergent period for these subjects will consist of periods: 1. From the first dose on the ponesimod start date up to the last dose prior to the pregnancy interruption +15 days, and

2. From the first dose of study drug after the pregnancy interruption up to EOT+ 15 days.

In order to assess events that occur during the pregnancy interruption, a new "pregnancy interruption emergent period" is defined as from the last dose prior to pregnancy interruption + 16 days to the minimum of (first dose after pregnancy interruption - 1 day, EOS date).

Treatment-emergent definitions are applicable to all safety variables, e.g., AEs, laboratory tests, pulmonary function tests (PFTs), vital signs and ECGs.

CONFIDENTIAL – FOIA Exemptions Apply in U.S. Status: Approved, Date: 20 September 2023

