5.2.1.5. Subject treatment completion status

A subject is considered to have completed treatment as per protocol in the core study if a treatment completion record is documented in SDTM201.DS, i.e., where DSSCAT = 'TREATMENT TERMINATION' and DSDECOD is equal to 'COMPLETED'. Date of completion is the date in DSSTDTC for this record.

A subject is considered to have prematurely discontinued from study treatment in the core study if a reason for premature treatment discontinuation or date of treatment discontinuation is documented in SDTM201.DS, i.e., where DSSCAT = 'TREATMENT TERMINATION' and DSDECOD is not equal to 'COMPLETED'. Date of discontinuation is the date in DSSTDTC for this record and reason for discontinuation is stored in DSDECOD.

Possible primary reasons for premature discontinuation of study treatment in the core study are 'Death', 'Adverse Event' and 'Other'. If the primary reason is 'Other', the specific reason is captured in DSTERM as free text.

A subject is considered to have completed treatment as per protocol in the extension study if a study completion record is documented in SDTM202.DS, i.e., where DSSCAT = 'TREATMENT TERMINATION' and DSDECOD is equal to 'COMPLETED'. Date of completion is the date in DSSTDTC for this record.

A subject who transitions to commercial study drug is considered to have completed study treatment as per protocol if DSSCAT = 'TREATMENT TERMINATION' and DSDECOD is equal to 'APPROVED DRUG AVAILABLE FOR INDICATION' in SDTM202.DS. Date of completion is the date in DSSTDTC for this record.

A subject is considered to have prematurely discontinued from study treatment in the extension study if:

• A permanent reason for discontinuation or date of discontinuation is documented in SDTM202.DS, i.e., where DSSCAT = 'TREATMENT TERMINATION' and DSDECOD is not equal to 'COMPLETED' or 'APPROVED DRUG AVAILABLE FOR INDICATION'. Date of discontinuation is the date in DSSTDTC for this record and the reason for discontinuation is stored in DSDECOD.

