5.3.1.2. ARR up to last treatment in the Analysis Period + 7 days

This endpoint was analyzed for the Interim Analysis and is not planned to be analyzed for the Final CSR, as noted below, in Section 5.3.2.4.

For subjects who completed the study at the end of an Analysis Period, who discontinued during an Analysis Period, or who had a treatment interruption between treatment periods, the Analysis Period end date may be up to 90 days after last intake of ponesimod in the Analysis Period.

To consider the on-treatment ARR, ARR up to last treatment date in the Analysis Period + 7 days is also derived.

The number of confirmed relapses and length of observation are derived as defined in Section 5.3.1.1 above, where end of the Analysis Period is capped at the minimum of [last treatment in the Analysis Period + 7 days, end of the Analysis Period] and only relapses with onset

in this period are included. The number of unconfirmed and confirmed (all) relapses is similarly derived.

ARR up to last treatment in the Analysis Period + 7 days is derived for AP3.

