6.14.5. Handling of missing and partially missing End-of-Treatment Dates

End-of-treatment date: the last drug administration date recorded on the study drug log.

If end date is missing on last record in SDTM.EC then:

• If the subject has discontinued early then date of last administration is taken as DS.DSSTDTC when DSSCAT = 'Study termination'.

If end date is partially missing on last record in SDTM.EC then:

• set as min(upper limit, DS.DSSTDTC where DSSCAT= 'Study termination',)

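### When the last-dose date is missing, the SAP substitutes the end-of-study date, which for a subject who completes safety follow-up falls 30 or 90 days after dosing stopped

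*SAP*

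**What the plan says.** SAP 5.4.1.1 covers a missing end date on the last EC record, giving loss to follow-up as an example: "then date of last administration is taken as DS.DSSDTC when DSSCAT = 'Study termination". The rule carries no other condition. SAP 6.14.5, on End-of-Treatment (EOT) dates, is narrower: "If the subject has discontinued early then date of last administration is taken as DS.DSSTDTC when DSSCAT = 'Study termination". For a partially missing date, 6.14.5 takes the earlier of the upper limit of the possible date and study termination.

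The study-termination record is the EOS record. SAP 5.1.1 has the extension EOS date "defined as DSSTDTC in SDTM202.DS, where DSSCAT='STUDY TERMINATION", replaced by the death date if the subject died. Protocol 3.1.1 fixes how far EOS lies from dosing: EOS2 "for an individual patient is reached 30 days after the last dose of study drug in TP1", and "EOS3 for an individual patient is reached 90 days after the last dose of study drug" for those who entered TP2 or TP3. SAP 5.3.1.2 acknowledges the gap: "the Analysis Period end date may be up to 90 days after last intake of ponesimod in the Analysis Period".

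A date closer to dosing is already in use. SAP 5.2.1.5 reads the TREATMENT TERMINATION record for premature discontinuation: "Date of discontinuation is the date in DSSTDTC for this record and the reason for discontinuation is stored in DSDECOD". The same section computes time to treatment discontinuation from it.

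**The concern.** The rule takes a date that the design puts after dosing and treats it as the last day of dosing. Several derivations depend on that day. Under SAP 5.1.4, "the treatment-emergent period is defined as the time from first administration of ponesimod up to 15 days (inclusive) after last administration of ponesimod". Exposure, proxy compliance, AE observation time, the last on-treatment value, the follow-up visit windows and the start of the post-treatment-emergent period all count from it as well.

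Two consequences matter most for interpretation.

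- **Off-drug values reported as on-treatment.** The last on-treatment value is the last one up to EOT plus 1 day. Protocol 1.3.2.2 reports lymphocyte counts back at baseline within 1 or 2 weeks of stopping, so a recovered count could be shown as the on-treatment value. Pulmonary function values are exposed in the same way.
- **Loss of the post-treatment period.** The SAP added the post-treatment relapse rate to look for disease reactivation. An affected subject contributes no time to it.

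The plan would also disagree with itself: the same subject could show exposure up to about 90 days longer than the time to treatment discontinuation.

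**Working it through.** **The plan's own figure.** Protocol 3.1.1 gives a maximum duration per patient of 649 weeks, from 636 weeks of treatment plus 90 days of follow-up: 636 + 90/7 = 648.86, which rounds to 649. So the 90-day gap between last dose and EOS is built into the design.

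**Inputs.**
- Gap g from true last dose to EOS: 30 days for TP1, 90 days for TP2/TP3 (Protocol 3.1.1), with visit windows of ±5 and ±7 days (Protocol Tables 2 and 3).
- Exposure = (end date − start date + 1)/365.25 (SAP 5.4.1.1).
- Treatment-emergent window ends at last dose + 15 days (SAP 5.1.4); AE observation time ends at the earlier of that day and EOS (SAP 5.4.4.2).
- Post-treatment-emergent period runs from last dose + 16 days to the last study date (SAP 5.1.6).
- Scale: 20 mg group at the 2019 interim, median exposure 8.02 years, 817 subject-years (Protocol 1.3.2.4).

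**Per affected subject who completes follow-up.** Set the true last dose at day 0 and EOS at day g. The rule moves the last dose to day g.

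| Quantity | TP1, g = 30 | TP2/TP3, g = 90 |
|---|---|---|
| Exposure error, g/365.25 | +0.082 y | +0.246 y |
| Range with visit windows | 25 to 35 days | 83 to 97 days |
| Share of 8.02 y | 1.0% | 3.1% |
| Observed treatment-emergent window ends on day | 15 becomes 30 | 15 becomes 90 |
| Days reclassified | 15 (Days 16-30) | 75 (Days 16-90) |
| Post-treatment-emergent days, g − 16 + 1 | 15 becomes 0 | 75 becomes 0 |

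The last row is 0 because the period would start at g + 16, after EOS at g. It is an empty period.

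**Group exposure.** The number affected is not stated, so it is an assumption here. For k affected subjects against 817 subject-years, the relative increase is k × g/365.25/817:
- k = 1: 0.01% (TP1) to 0.03% (TP2/TP3)
- k = 5: 0.05% to 0.15%
- k = 10: 0.10% to 0.30%
- k = 20: 0.20% to 0.60%

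**Other derivations, read side by side.**
- AEs per 100 subject-years: events and observation time both rise, so the direction of bias is undetermined. Frequency tables can only gain treatment-emergent events.
- Follow-up visits FU7, FU30 and FU90 (SAP 5.1.8) are windowed on days since last dose, so genuine follow-up visits no longer map to them.
- Proxy compliance (SAP 5.4.1.2) is overstated, because the off-drug tail is counted as dosed time.
- Relapse rate and time to first relapse to the end of AP3 run to the last study date (SAP 5.1.9, 5.3.1.1, 5.3.1.3) and do not change.

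**Consistency of the rules.** SAP 5.4.1.1 is unconditional and names DSSDTC; 6.14.5 is limited to early discontinuers and names DSSTDTC. A subject who moved to commercial drug counts as having completed treatment (SAP 5.2.1.5), so with a missing end date only 5.4.1.1 would apply. SAP 5.1.1, read alone, takes the latest end date recorded on the drug log. The effect on treatment-emergent status therefore rests on 6.14.5.

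**The case against.** **The fixed gap does not describe most of the subjects the rule targets.** This stands. The 30- or 90-day interval holds for those who complete safety follow-up. They are also due an EOT visit within 5 days of the last dose, so their drug-log end date is perhaps the least likely to be missing. For a subject lost to follow-up the interval is not fixed and few late events would be on file to reclassify. For a death, EOS is the death date and the gap may be near zero. A reader might infer that every drop-out is shifted by 30 to 90 days; the documents do not support that.

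**Not every output is affected.** This also stands. Besides the AP3 relapse analyses, disability-progression censoring uses the last EDSS assessment without an increase, not EOT. The post-treatment DMT category also admits a therapy ongoing at EOS, so that criterion is met whichever EOT is used, although entry to the Follow-up Phase could still be lost. One could compute a post-treatment length of −15 days from end − start + 1, but that only applies a formula to an empty period. Partial dates are already limited by the last day of the known month or year, so with only the day missing the error is at most about 30 days.

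**The rule is conservative, like the SAP's other conventions.** The SAP treats missing AE intensity as severe, missing relationship as related, missing seriousness as serious, and unclear onset as treatment-emergent. This defence fails. The rule also adds off-drug time to exposure and to the AE-rate denominator, lets recovered values pass as on-treatment, and empties the period meant to detect reactivation.

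**The alternative date is not guaranteed.** Fair: no section says the treatment-termination date equals the last dose, or that it is filled in when the drug log is not. A fallback is needed.

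**Conclusion.** The rule is wrong as written. It assigns a last-dose date that the protocol places after dosing, while a date meant to mark the end of treatment goes unused. For an affected subject who completed follow-up, the error is about 30 days (TP1) or 90 days (TP2/TP3) of exposure, 15 or 75 days of events reclassified as treatment-emergent, and complete loss of post-treatment-emergent time.

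The reach is limited. The number affected is not given and could be zero, the effect on group totals is probably small, and all objectives are exploratory. The conclusion assumes that 6.14.5 governs the EOT date used for treatment-emergent status, and the per-subject figures assume that the EOS visit took place as scheduled. The point is worth correcting because it puts a known misclassification into the safety outputs and the repair is cheap.

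**What to change.** In SAP 5.4.1.1 and 6.14.5:

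1. For a missing last-dose date, use the earlier of DSSTDTC where DSSCAT = 'TREATMENT TERMINATION' and the study-termination date.
2. For a partial date, use the earlier of its upper limit and the date from step 1.
3. If the treatment-termination date is also missing, use the last documented dosing date, supported by the dispensing dates listed under SAP 5.4.2.3 and no later than study termination. Do not subtract the scheduled follow-up: for a subject who died or was lost while on drug, that would remove real exposure and move on-treatment events to the post-treatment period.
4. Report the number of subjects with an imputed date, by treatment group.
5. Reconcile the two sections: one condition, one variable name (DSSDTC or DSSTDTC), and a cross-reference from the EOT definition in 5.1.1.

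The cost is one variable reference and a short fallback in two sections, plus one count in the exposure output. No new data are needed.
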